5.2. Primary Efficacy Endpoint(s)

5.2.1. Definition

RSV RNA viral load will be measured in mid-turbinate nasal swab specimens using an RSV A/B qRT-PCR assay.

The primary efficacy endpoint is the RSV RNA viral load area under the curve (AUC) from immediately prior to first dose of study drug (baseline) through Day 5 (AUC_{Day 5}) derived from the RSV RNA viral load as measured by a qRT-PCR assay in nasal swabs.

5.2.2. Estimand

The primary efficacy endpoint is the RSV RNA viral load AUC_{Day 5} in subjects from both cohorts (hospitalized and outpatient). The presence of a dose-response will be established using the model-based trend test (MCP-Mod) among two doses of JNJ53718678 versus treatment with placebo, in combination with SOC.

The primary estimates of the AUC_{Day 5} will be derived from a mixed model (see Section 5.2.3 for the detailed specification). No explicit imputations of missing data from nasal swabs post-baseline will be done in this model, as this mixed model would allow to make inferences implicitly imputing the missing data under the missing at random assumption.

5.2.3. Analysis Method

Mean \log_{10} RSV RNA viral load values over time will be analyzed using a restricted maximum likelihood based repeated measures approach (MMRM). The analysis model includes fixed (discrete) effect parameters for treatment, randomization stratification factors (derived), analysis visit and treatment-by-analysis visit interaction, as well as continuous covariates for baseline \log_{10} viral load and baseline \log_{10} viral load-by-analysis visit interaction. An unstructured (co)variance structure will be used to model the within-subject errors. In case this model will not converge, the Toeplitz covariance structure will be applied. The Kenward-Roger approximation will be used to estimate the denominator degrees of freedom.

For subgroup analyses, the model will also include the subgroup variable as a covariate and the subgroup-by-treatment, subgroup-by-analysis visit and subgroup-by-analysis visit-by-treatment interactions. For details about subgroups please see Section 2.4.

A generalized MCP-Mod (1) approach at 1-sided alpha-level of 2.5% will be applied based on the estimated AUC treatment group effect and variance covariance matrix. Candidate models are given by the EMax (0.40428), Exponential (0.36411) and Linear model, with the aim to test for existence of drug-related effects. Each of the dose-response shapes in the candidate set will be tested using the corresponding contrast t-test statistic, employing a critical value derived for the maximum of the t-test statistics (based on the associated multivariate t-distribution) to ensure appropriate multiplicity correction that preserves a 1-sided 0.025 Type I error rate. A dose-response trend is established when the maximum of the t-test statistics exceeds the critical value.

MCP-Mod uses dose levels 0, 3 and 9 mg/kg which correspond to Placebo, Low and High dose respectively according to the dose/kg for age-group 3 as described in Section 1.2.

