 - Age groups 1, 2, and 3: matching placebo (volume of placebo suspension to match the calculated volume of the JNJ-53718678 suspension for the high dose)
 - Low volume placebo:
 - Age groups 1, 2, and 3: matching placebo (volume of placebo suspension to match the calculated volume of the JNJ-53718678 suspension for the low dose)

Post-amendment #4 (dated 26 May 2020): Cohort 1 enrollment complete with all randomized and treated subjects receiving once daily dosing for a planned treatment duration of 7 days. Cohort 2 enrollment continuing with study drug to be administered twice daily (*bis in die* [BID]) for a planned treatment duration of 7 days. Total planned 14 doses are based on bodyweight and age group, but total daily dose remains identical for both cohorts regardless of dosing regimen:

- High Dose (Cohort 2: n = 50 [target]):
 - Age group 1: 2.5 mg JNJ-53718678/kg bodyweight
 - Age group 2: 3.0 mg JNJ-53718678/kg bodyweight
 - Age group 3: 4.5 mg JNJ-53718678/kg bodyweight
- Low Dose (Cohort 2: n = 50 [target]):
 - Age group 1: 0.85 mg JNJ-53718678/kg bodyweight
 - Age group 2: 1.0 mg JNJ-53718678/kg bodyweight
 - Age group 3: 1.5 mg JNJ-53718678/kg bodyweight

- Placebo (Cohort 2: n = 50 [target]): those randomized to a placebo regimen will subsequently be randomized 1:1 to receive either:
 - High volume placebo:
 - Age groups 1, 2, and 3: matching placebo (volume of placebo suspension to match the calculated volume of the JNJ-53718678 suspension for the high dose)
 - Low volume placebo:
 - Age groups 1, 2, and 3: matching placebo (volume of placebo suspension to match the calculated volume of the JNJ-53718678 suspension for the low dose)

For analysis purposes, treatment groups will be analyzed and presented regardless of dosing regimen (QD or BID).

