1.5. Randomization and Blinding

Central randomization will be implemented in this study. The codes will be maintained within the IWRS, which has the functionality to allow the investigator to break the blind for an individual subject. Within each cohort (including the subcohort of Cohort 1), eligible subjects will be randomized 1:1:1 to receive either a low or a high dose of JNJ-53718678, or placebo. Those randomized to a placebo regimen will be subsequently randomized in a 1:1 ratio to receive either low or high volume of placebo. This results in an overall randomization scheme of 2:2:1:1 (low dose JNJ-53718678, high dose JNJ-53718678, low volume placebo, high volume placebo). Randomization will be based on a computer-generated randomization schedule prepared before the study by or under the supervision of the sponsor.

In the subcohort of Cohort 1, next to randomization to treatment group, within each treatment arm (high dose, low dose, placebo), the 6 subjects will be randomized 1:1 to 1 of 2 different PK sampling groups. In Cohort 1, next to randomization to treatment group, the first 12 subjects of each age group (subcohort not included) will be randomized 1:1 to 1 of 2 different PK sampling groups. Once 12 subjects of a particular age group have been randomized to the 2 different PK sampling groups, the investigator can assign the subsequently enrolled subjects to either of the 2 PK sampling groups, but preferably alternating between 2 different PK sampling groups.

The randomization will be balanced by using randomly permuted blocks and will be stratified by time since symptom onset at randomization (≤ 3 days and >3 days) and by presence of risk factors for severe RSV disease (otherwise healthy vs presence of [a] risk factor[s] for severe RSV disease as defined above). Stratification will be applied to each cohort separately, with exception of the subcohort. Subjects with symptom onset ≤ 3 days before randomization must account for at least 45% of all enrolled subjects in Cohorts 1 and 2. To guarantee the required balance between strata for the interim analyses, enrollment in >3 days to ≤ 5 days since symptom onset stratum might be temporarily paused prior to an interim analysis and stopped prior to the final analysis.

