5.1. Analysis Specifications

Primary, secondary and exploratory efficacy analyses described in the following sections will be analyzed and presented using primarily the ITT-i analysis set, unless otherwise specified.

Analyses will be performed combining Cohort 1 (hospitalized subjects) and Cohort 2 (outpatients subjects) as well as in each cohort separately except for IA#1 where data from subjects in Cohort 1 only are available. In each IA, the cohort/s information to be considered for decision-making is specified in Section 5.6. For subgroup analysis, please refer to Section 2.4 for further details.

For all the stratified statistical analyses, the derived randomization stratification factors (symptom onset [≤ 3 days vs >3 days to ≤ 5 days before randomization] and presence of risk factors for severe RSV disease [Yes vs No]) will be used instead of the randomization stratification factors as collected in IWRS. Exception is sensitivity analysis of the primary efficacy endpoint based on IWRS randomization stratification factors.

In addition to the analyses outlined in the subsequent sections, efficacy parameters and a selection of derived efficacy variables will be presented in by-subject data listings.

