Based on the binary categorization:

- Detectable or quantifiable = Yes (1)
- Undetectable = No (0)

the difference in proportion of undetectable between each active treatment group as compared to placebo will be investigated. Frequency procedure in SAS® provides Newcombe confidence limits with Mantel-Haenszel weights for the common risk difference, controlling for the two randomization stratification factors (separately). The

difference in proportion of undetectable and 95% 2-sided confidence interval for this point estimate, controlling for randomization stratification factors, will be presented.

The aforementioned will be presented overall by treatment group and by the subgroups as defined in Section 2.4.

Time to Virus Undetectable [time to event]

With reference to the two time to event approaches, their definitions and derivations detailed in Section [5.3.1.1](#):

The time to event variables will be analyzed using Kaplan-Meier analysis (for both approaches). A summary table including number of subjects included in the analysis, number of subjects censored, 25th and 75th percentiles and median time to event, with 95% 2-sided confidence intervals based on Kaplan-Meier transformation method, will be presented by treatment group. The data will be presented graphically using the Kaplan-Meier estimate of the survival function by treatment group.

The aforementioned will be presented overall by treatment group and by the subgroups as defined in Section 2.4, for time (hours) to **confirmed undetectable** viral load only.

As sensitivity analysis, overall summary tables will be presented as described above for time (hours) to **confirmed undetectable** viral load but excluding nasal swab samples as previously described (refer to Section [5.2.3](#)).

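### The pooled primary viral-load model leaves out cohort, although subjects are randomized within cohort; the cost is an overstated standard error and a conservative trend test

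*SAP*

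**What the plan says.** Section 5.2.2 sets the primary estimand "in subjects from both cohorts (hospitalized and outpatient". Section 5.2.3 gives the model: "The analysis model includes fixed (discrete) effect parameters for treatment, randomization stratification factors (derived), analysis visit and treatment-by-analysis visit interaction". Baseline log10 viral load and its interaction with visit complete it. The estimated AUCs and their covariance matrix then go into the MCP-Mod trend test.

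Section 5.1 defines the derived stratification factors. It names symptom onset "and presence of risk factors for severe RSV disease [Yes vs No]) will be used instead of the randomization stratification factors" recorded in IWRS. Cohort is not among them.

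On the design side, Section 1.5 says that within each cohort "eligible subjects will be randomized 1:1:1 to receive either a low or a high dose of JNJ-53718678, or placebo", and adds: "Stratification will be applied to each cohort separately, with exception of the subcohort". Section 1.4 considers that viral-load means or variability may be inconsistent between cohorts.

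Cohort does appear elsewhere:
- Section 5.1: "Analyses will be performed combining Cohort 1 (hospitalized subjects) and Cohort 2 (outpatients subjects) as well as in each cohort separately".
- Table 8 lists it as a subgroup for viral load.
- Section 5.3.2.1 lists it among the candidate predictors of viral-load change, and strong predictors may then be tried as extra covariates in the primary model.

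None of the three sensitivity analyses in Section 5.2.3.1 adds it.

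**The concern.** Cohort is a group within which the trial randomizes, and it separates children ill enough to be in hospital from those at home. If viral load runs a different course in the two groups and the model has no cohort term, the difference is counted as residual variation. Because the arms are balanced within cohort, that variation does not actually affect the treatment contrast. The reported standard error is therefore larger than the true sampling error, and the MCP-Mod statistics are too small.

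The primary test is at stake, and so are the interim viral-load tests on combined cohorts in Section 5.6: the futility trend test at IA#2 and the conditional power at IA#3. At IA#3 the observed statistics enter twice, through the conditional type I error and through the projected second-stage mean. If the drug works, an overstated standard error pushes the viral-load criterion towards futility or enrichment.

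**Working it through.** **Inputs.** From Section 1.4: 20% reduction in AUC, CV 35%, one-sided alpha 2.5%, 48 and 50 subjects per arm in Cohorts 1 and 2 (144 + 150 = 294). From Section 5.2.3: doses 0, 3 and 9; Emax parameter 0.40428; exponential parameter 0.36411; linear shape. The cohort difference d, in residual SDs, is an assumption, because the SAP gives none. It means the difference left after baseline viral load, symptom onset and risk factor.

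**Step 1: reproduce Table 1.** Max-t test with optimal contrasts, top-dose effect 0.20/0.35 = 0.571 SD, critical value by Monte Carlo. Power at CV 35% (linear / Emax / exponential):

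| N per arm | Table 1 | Recomputed |
|---|---|---|
| 74 | 92.3 / 95.3 / 96.6 | 92.3 / 95.3 / 96.6 |
| 50 | 79.0 / 84.0 / 86.9 | 79.0 / 83.9 / 86.8 |
| 24 | 47.1 / 51.2 / 54.7 | 47.0 / 51.1 / 54.7 |

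All cells agree within 0.1 point. The calculation that reproduces the table uses one common CV and no between-cohort component.

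**Step 2: inflation of the reported standard error.** With cohort share p = 144/294 = 0.490, p(1 − p) = 0.2499. The omitted difference adds d² × p(1 − p) to a residual variance of 1, so the ratio is sqrt(1 + d² × 0.2499).
- d = 0.25: sqrt(1.0156) = 1.008, or +0.8%
- d = 0.5: sqrt(1.0625) = 1.031, or +3.1%
- d = 1.0: sqrt(1.2499) = 1.118, or +11.8%

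Dividing 294 by the squared ratio gives an equivalent sample of about 289, 277 and 235.

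**Step 3: effect on the specified test.** AUC values were simulated (40,000 trials per scenario) with exact 1:1:1 allocation within cohort. They were analysed with the max-t critical value, without and with a cohort term. Linear shape, CV 35%:

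| N per arm | d | Power without / with cohort (%) | Size without / with cohort (%) |
|---|---|---|---|
| 98 | 0 | 97.5 / 97.5 | 2.3 / 2.3 |
| 98 | 0.5 | 96.9 / 97.4 | 2.1 / 2.5 |
| 98 | 1.0 | 95.3 / 97.4 | 1.3 / 2.6 |
| 74 | 0 | 92.3 / 92.3 | 2.4 / 2.4 |
| 74 | 0.5 | 91.3 / 92.3 | 2.1 / 2.4 |
| 74 | 1.0 | 88.1 / 92.4 | 1.3 / 2.4 |

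Monte Carlo error on a size of 2.5% is sqrt(0.025 × 0.975 / 40,000), about 0.08 point. With the term, power does not depend on d.

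**Step 4: IA#3.** With the approximate counts in Section 5.2.3.2 (144 and 75), p = 144/219 = 0.658 and p(1 − p) = 0.225. The inflation is sqrt(1 + 0.25 × 0.225) = 1.028 at d = 0.5 and sqrt(1.225) = 1.107 at d = 1.0.

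**The case against.** The strongest reply is that validity is not touched. Allocation is 1:1:1 within cohort, the trial is exploratory by the SAP's own account, and at 98 per arm power remains 95.3% even at d = 1.0. Baseline viral load, its interaction with visit, symptom onset and risk factor are already in the model and will absorb part of any raw cohort difference, so the upper end of the range is hard to justify. All of this stands, and it limits the point to efficiency.

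Nor is cohort ignored. The by-cohort and subgroup analyses are prespecified, and Section 5.3.2.1 offers a route to adjustment. That route is optional and chosen after seeing the data, so it does not repair the pooled primary test.

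Section 1.4 raises inconsistency between cohorts per treatment group as a reason not to combine them. An additive cohort term deals only with a shift in means, not with unequal variability or a treatment effect that differs by cohort.

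Three stronger readings are tempting but not supported:
- A reader might infer bias or an inflated type I error. Balance within cohort argues against the first, and the simulated size goes down, not up.
- A reader might want a further level for once-daily versus twice-daily dosing in Cohort 2. That split comes from a protocol amendment and is not a randomization stratum, and Section 1.2 states: "For analysis purposes, treatment groups will be analyzed and presented regardless of dosing regimen (QD or BID".
- A reader might extend the point to the risk differences, computed "controlling for the two randomization stratification factors (separately", and ask for fully crossed strata. That is a different question. Crossing a three-level cohort and regimen factor with onset and risk factor gives 3 × 2 × 2 = 12 cells, about 98/12 = 8 subjects per arm each, with sparse cells likely.

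**Conclusion.** The omission is real for the pooled primary MMRM, and nothing else in the SAP repairs it. Its effect is an overstated standard error and a conservative trend test: small if the residual cohort difference is 0.5 SD or less (standard error up to about 3.1%, at most about one power point), and more noticeable near 1.0 SD (11.8%; about two power points at 98 per arm and four at 74).

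These figures rest on an assumed cohort difference, a common residual variance, exact balance within cohort, and a linear model for AUC standing in for the MMRM with complete data. They do not carry over to the AFT models, for which no size is claimed. The case for the change is that it costs almost nothing and matches the analysis to the way subjects were allocated.

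**What to change.** In Section 5.2.3, add cohort (two levels) and cohort-by-visit as fixed effects in the pooled MMRM. State that the same model is used wherever Section 5.6 tests viral load on combined cohorts. Where an AFT model is fitted to both cohorts together (Sections 5.3.2.1 and 5.3.2.2), add cohort as a covariate. Models fitted to one cohort, including those for hospitalized subjects in Section 5.3.2.3.2, need no change.

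The cost is a few lines of SAP wording and a few degrees of freedom. The subgroup version of the MMRM already includes a subgroup-by-visit term, so little new programming is needed. The change should be written in before database lock, so that adjustment for cohort does not depend on the later predictor search.

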5.2.3.1. Sensitivity Analyses

Utilizing the same methodology as described for the primary efficacy endpoint, three sensitivity analyses will be performed as follows:

- MMRM + MCP-Mod: repeat analysis but using IWRS randomization stratification factors in the model as opposed to the derived factors based on the collected eCRF data.
- MMRM + MCP-Mod: repeat analysis but using the PP analysis set (if >10% ITT-i subjects excluded from PP analysis set due to major protocol deviations).
- MMRM + MCP-Mod: repeat analysis but excluding nasal swab samples where:
 - Ribonuclease P (RNase P [housekeeping gene]): result = Target Not Detected AND
 - RSV A: result = Target Not Detected AND
 - RSV B: result = Target Not Detected

5.2.3.2. Methods to Control the Type I Error for Multiplicity and Adaptations

Due to the adaptive design, and multiple populations (i.e. full ITT-i analysis set and sub-population based on ITT-i subjects with symptom onset [≤ 3 days relative to randomization]), the Type I error will be controlled using the inverse-normal p-value-combination test as a secondary analysis approach. The total study alpha will be used at the timepoint for the primary analyses which are:

[figure not shown]
- Interim analysis 4 for antiviral effects ($\alpha=5\%$, i.e. 2.5% 1-sided)
- Final analysis for clinical course endpoints ($\alpha=20\%$, i.e. 10% 1-sided)

In a sequential testing framework, this corresponds to the following cumulative α -spending on primary and secondary endpoints:

	IA#1	IA#2	IA# 3	IA#4	Final Analysis
Viral load	0%	0%	0%	5%	5%
Clinical course	0%	0%	0%	0%	20%

This testing procedure will be applied on the ITT-i set

The primary endpoint on viral load ($AUC_{Day\ 5}$) will be tested at alpha of 5% (i.e. 2.5% 1-sided). To account for multiplicity in the statistical evaluation of the key clinical course secondary endpoints, a Bonferroni-Holm procedure will be applied to control for the overall Type I error rate. Clinical course endpoints are tested using an MCP-Mod test at 1-sided alpha level of 10%. Testing of the key clinical course endpoints (time to resolution of key RSV symptoms [ObsRO], incidence of RSV-related complications and change from baseline in key RSV symptoms [ObsRO]) will therefore be started at the 20/3 (6.667)% level. Levels used for testing will be adjusted, in case at least one of the key clinical course endpoints succeeds. The testing strategy is graphically summarized as:

The family wise error rate is strictly controlled at a level below 20% using the considered Bonferroni-Holm procedure.

The study design allows for enrichment at interim analyses 2, 3 and 4. The sample size re-estimation for clinical course endpoints will be conducted at interim analysis 3 only. To control for the multiple potential adaptations (enrichment and sample size re-estimation), the following procedures will be applied. All computations are to be conducted using stage-wise **1-sided** p-values. The final test decision is based on 2-sided p-values. Given the final 1-sided p-value, the 2-sided p-value results as:

- $p_{2\text{-sided}} = 2 \times \min\{p_{\text{reported}}, 1 - p_{\text{reported}}\}$

Let the cumulative sample sizes for Cohort i up to analysis j be defined as n_{ij} :

	IA#1	IA#2	IA#3	IA#4	Final Analysis
Cohort 1 (n=144)	n_{11} (~36)	n_{12} (~75)	n_{13} (~144)	n_{14} (~144)	n_{15} (~144)
Cohort 2 (n=150)		n_{22} (~36)	n_{23} (~75)	n_{24} (~150)	n_{25} (~300)

RSV RNA Viral Load:

The total sample size planned for the primary analysis on viral load is given as: $n_{\text{Primary}}=294$. This constitutes the sample size of both Cohorts 1 and 2.

Stagewise weights and 1-sided p-values are defined as:

	IA#2	IA#3	IA#4
No enrichment:			
Weight	1		
p-value	p_{14}^F		
Final p-value (global)	p_{14}^F		
Final p-value (sub)	p_{14}^S		
Enrich at IA#2:			
Weight (w_{ij})	$(n_{12}+n_{22})/n_{\text{Primary}}$	$(n_{\text{Primary}} - n_{12} - n_{22})/n_{\text{Primary}}$	
p-value	p_{12}^F	p_{34}^S	
Final p-value (global)	$1 - \Phi \left(\sqrt{w_{12}} \Phi^{-1}(1 - p_{12}^F) + \sqrt{w_{34}} \Phi^{-1}(1 - p_{34}^S) \right)$		

	IA#2	IA#3	IA#4
Final p-value (sub)	$1 - \Phi \left(\sqrt{w_{12}} \Phi^{-1}(1 - p_{12}^S) + \sqrt{w_{34}} \Phi^{-1}(1 - p_{34}^S) \right)$		
Enrich at IA#3:			
Weight (w_{ij})	$(n_{13}+n_{23})/n_{Primary}$	$(n_{Primary}-n_{13}-n_{23})/n_{Primary}$	
p-value	p_{13}^F	p_{44}^S	
Final p-value (global)		$1 - \Phi \left(\sqrt{w_{13}} \Phi^{-1}(1 - p_{13}^F) + \sqrt{w_{44}} \Phi^{-1}(1 - p_{44}^S) \right)$	
Final p-value (sub)		$1 - \Phi \left(\sqrt{w_{13}} \Phi^{-1}(1 - p_{13}^S) + \sqrt{w_{44}} \Phi^{-1}(1 - p_{44}^S) \right)$	

- p_{ij}^F defines the p-value for the MCP-Mod test for data collected from in stages i to j in the full population
- p_{ij}^S defines the p-value for the MCP-Mod test for data collected from in stages i to j in the sub population

A p-value combination for the test of the sub-population is required, as the enrichment decision implies a sample size re-calculation for the sub-population.

Clinical Course Endpoints:

Sample size for clinical course endpoints is only based on Cohort 2. Let $n_{Primary} = 225$ be defined as midway between planned ($N= 150$) and maximum sample size ($N=300$).

	IA#2	IA#3	IA#4	Final Analysis
No enrichment:				
Weight (w_{ij})	$(n_{23})/n_{Primary}$		$(n_{Primary}-n_{23})/n_{Primary}$	
p-value	p_{23}^F		p_{45}^F	
Final p-value (global)	$1 - \Phi \left(\sqrt{w_{23}} \Phi^{-1}(1 - p_{23}^F) + \sqrt{w_{45}} \Phi^{-1}(1 - p_{45}^F) \right)$			
Final p-value (sub)	$1 - \Phi \left(\sqrt{w_{23}} \Phi^{-1}(1 - p_{23}^S) + \sqrt{w_{45}} \Phi^{-1}(1 - p_{45}^S) \right)$			
Enrich at IA#2:				
Weight (w_{ij})	$n_{22}/n_{Primary}$	$(1-w_{22})* (n_{23}-n_{22})/(n_{Primary}-22)$		$(1-w_{22})* [(n_{Primary}-n_{23})/(n_{Primary}-n_{22})]$
p-value	p_{22}^F	p_{33}^S	p_{45}^S	
Final p-value (global)	$1 - \Phi \left(\sqrt{w_{22}} \Phi^{-1}(1 - p_{22}^F) + \sqrt{w_{33}} \Phi^{-1}(1 - p_{33}^S) + \sqrt{w_{45}} \Phi^{-1}(1 - p_{45}^S) \right)$			
Final p-value (sub)	$1 - \Phi \left(\sqrt{w_{22}} \Phi^{-1}(1 - p_{22}^S) + \sqrt{w_{33}} \Phi^{-1}(1 - p_{33}^S) + \sqrt{w_{45}} \Phi^{-1}(1 - p_{45}^S) \right)$			
Enrich at IA#3:				
Weight (w_{ij})	$n_{23}/n_{Primary}$		$(n_{Primary}-n_{23})/n_{Primary}$	
p-value	p_{23}^F		p_{45}^S	
Final p-value (global)	$\sqrt{w_{23}} \Phi^{-1}(1 - p_{23}^F) + \sqrt{w_{45}} \Phi^{-1}(1 - p_{45}^S)$			
Final p-value (sub)	$\sqrt{w_{23}} \Phi^{-1}(1 - p_{23}^S) + \sqrt{w_{45}} \Phi^{-1}(1 - p_{45}^S)$			

	IA#2	IA#3	IA#4	Final Analysis
Enrich at IA#4:				
Weight (w_{ij}) ^{\$}	$n_{23}/n_{\text{Primary}}$	$(1-w_{23})*(n_{24}-n_{23})/(n_{25,\text{Replan}}-n_{23})$	$(1-w_{13})*(n_{25,\text{Replan}}-n_{24})/(n_{25,\text{Replan}}-n_{23})$	
p-value	p_{23}^F	p_{44}^F		p_{55}^S
Final p-value (global)		$1 - \Phi \left(\sqrt{w_{23}} \Phi^{-1}(1 - p_{23}^F) + \sqrt{w_{44}} \Phi^{-1}(1 - p_{44}^F) + \sqrt{w_{55}} \Phi^{-1}(1 - p_{55}^S) \right)$		
Final p-value (sub)		$1 - \Phi \left(\sqrt{w_{23}} \Phi^{-1}(1 - p_{23}^S) + \sqrt{w_{44}} \Phi^{-1}(1 - p_{44}^S) + \sqrt{w_{55}} \Phi^{-1}(1 - p_{55}^S) \right)$		

\$ The denominator changes as we have the new sample size. The planned sample size is covered in w_{23} and $(1-w_{23})$. If study continues, the two new portions are identified as total n_{25} and (replan- n_{23}) subjects.

In case of no sample size increase, the IA#4 will coincide with the final analysis. In this situation, no enrichment at IA#4 is possible, such that either “no enrichment”, “enrich at IA#2” or “enrich at IA#3” will apply with p-values defined therein.

